6.4 Withdrawal of individual subjects

Subjects can leave the study at any time for any reason if they wish to do so without any consequences. The investigator can decide to withdraw a subject from the study for urgent medical reasons.

6.5 Replacement of individual subjects after withdrawal

In case of drop-outs, patients will not be replaced by including extra patients because feasibility of patient enrollment is one of the primary outcomes of this study. This also includes patients with an infection at T1 and thereby an exclusion for the biopsy.

7. SAFETY REPORTING

7.1 Temporary halt for reasons of subject safety

In accordance to section 10, subsection 4, of the WMO, the sponsor will suspend the study if there is sufficient ground that continuation of the study will jeopardise subject health or safety. The sponsor will notify the accredited METC without undue delay of a temporary halt including the reason for such an action. The study will be suspended pending a further positive decision by the accredited METC. The investigator will take care that all subjects are kept informed.

7.2 AEs, SAEs and SUSARs

7.2.1 Adverse events (AEs)

Adverse events are defined as any undesirable experience occurring to a subject during the study, whether or not considered related to the experimental intervention. For this study, all exercise-related AE's and AE's related to the biopsy (T1) and blood sampling (T0 en T1) reported spontaneously by the subject or observed by the investigator or his staff will be recorded.

In case a subject (with 3-weekly AC chemotherapy cycles) receives a prescription for G-CSF (pegfilgrastim) prior to the second cycle of chemotherapy (in case of neutropenia) this

will be reported by the coordinating researcher, because this might interfere with the secondary outcomes on immune function.

7.2.2 Serious adverse events (SAEs)

In this study, the sponsor will report only the SAEs related to the exercise intervention, the blood sampling (T0 en T1) and the biopsy (T1). The sponsor will report these specific SAE's through the web portal *ToetsingOnline* to the accredited METC that approved the protocol, within 7 days of first knowledge for SAEs that result in death or are life threatening followed by a period of maximum of 8 days to complete the initial preliminary report. All other SAEs will be reported within a period of maximum 15 days after the sponsor has first knowledge of the serious adverse events.

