Objective: To 1) ***study trial feasibility*** in terms of patient enrollment and the percentage of tumor biopsies that can be examined successfully, and 2) ***generate preliminary data*** on the potential effects of exercise on immune function assessed in the tumor and in blood.

Study design: Multicenter randomised controlled feasibility trial

Study population: 20 adult patients who are scheduled for neoadjuvant chemotherapy consisting of 4 cycles of 2 or 3-weekly adriamycin/cyclofosfamide (AC), followed by 12 weekly cycles of paclitaxel (T) weekly +/- trastuzumab, for early (stage I-III) breast cancer.

Intervention: 6-week (during 2 or 3 treatment cycles) moderate to high intensity aerobic and resistance exercise program supervised by a specifically educated physical therapist.

Main study parameters/endpoints: Trial feasibility and preliminary effects on immune function. Measurements will take place at baseline (prior to chemotherapy) and after 2 or 3 cycles (6 weeks).

Nature and extent of the burden and risks associated with participation, benefit and group relatedness: Prior to start of treatment, a diagnostic biopsy (part of routine care), a blood sample and a fitness test will be performed in all participants. At this time point the

blood sample collection and fitness test will be combined in one visit. After two (3-weekly) or three (2-weekly) cycles of AC chemotherapy an additional biopsy and blood sample will be taken and patients will perform a fitness test. The risks of the blood drawing and fitness test are negligible. The risk of clinically relevant complications of a breast tumor biopsy was around 0,2% in a multi-institutional study in 1994 [8]. Nowadays, the risk of complications is even lower, due to technological improvements that are implemented. The biopsies are necessary to study the effect of an exercise intervention on tumor and infiltrating immune cells. The safety of the exercise intervention has well been documented [9].

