- Upper and lower body muscle strength will be assessed with the 1RM leg press and bench press according to standardized protocols.

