6.3 Study procedures

After providing informed consent (IC), patients will be randomized in either the intervention or waitlist control group.

Participants in the intervention group will attend supervised exercise sessions twice a week at a local physical therapist and are encouraged to be physically active for at least 30 minutes per day at Borg level 12-14 (see paragraph 5.1).

Participants in the control group are requested to maintain their usual daily physical activities and are offered supervised exercise sessions after 6 weeks at the expense of the study budget (see paragraph 5.1).

Study parameters will be assessed at baseline (before start of chemotherapy) and after 6 weeks of chemotherapy (2 3-weekly or 3 2-weekly cycles) in the patient's own treating hospital. When patients are included from the Amstelland hospital they will be asked beforehand to come to the Amsterdam UMC – location VUmc for the physical test, blood samples and biopsy. Consequently, Amstelland will be a recruiting hospital in this study.

During the visits, information on physical fitness and blood samples will be collected. In addition, during the visit on T1 a tumor biopsy will be obtained. The T1 biopsy and physical fitness test will not be performed on the same day, as this might lead to contamination of the results on immunoreactivity in blood and tumor. We will strive to perform the physical fitness tests prior to the 3th (3-weekly) or 4th (2-weekly) chemotherapy administration so patients don't have to come to the hospital an extra time.

The visit on T0 will last approximately 75 minutes, the first visit on T1 (biopsy and blood sample) approximately 30 minutes and the second visit on T1 (physical fitness test) approximately 45 min.

Questionnaires will be sent to the participant's home and will take up to 10 minutes to complete, based on 6 items per minute. Questionnaires will be sent in paper only. Table 1 presents a summary of all study parameters.

	Measurement tool	-1	T0	T1
Primary outcome measurement				
Recruitment		X		
Quality of tumor material	Tumor biopsy		X	X
Secondary outcome measurement				
Clinical data				
Extent of the tumor	Medical records		X	
Disease, treatment and toxicity	Medical records		X	X
Performance status	Medical records		X	X
Co-morbidities and co-medication	Medical records		X	
Physical tests				
Aerobic fitness	Steep ramp test & endurance test		X	X
Muscle strength	1 RM legpress and 1 RM bench press		X	X
BMI	Height		X	
	Weight		X	X

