The first blood sample of 20ml will be drawn prior to the start of chemotherapy and randomization (T0), and the second blood sample of 24ml after 2 (3-weekly) or 3 (2-weekly) cycles of chemotherapy (T1). The second blood sample will be taken before the biopsy to be able to determine levels of thrombocytes and neutrophils. In case values of thrombocytes are $\leq 50 \times 10^9/L$ and/or neutrophils (ANC) are $\leq 0.5 \times 10^9/L$, patients will be excluded for the second biopsy because of an increased risk of procedure related hemorrhage or infection. Blood samples will be collected in 10ml heparin tubes without gel. Both blood samples will be drawn in the patient's own treating hospital, except for patients from the Amstelland hospital.

Blood samples will be centrifuged and PBMC's will be isolated before storage at -80° in the Tumor Immunotherapy laboratory of the Cancer Center Amsterdam for the duration of this study.

Blood samples – IL-6

Patients included from the Amsterdam UMC and randomized to the intervention group will be asked for consent to draw blood samples prior to and directly after one of the exercise sessions to examine acute exercise responses. This will be done with an extra informed

consent form. If patients prefer not to participate in this extra blood sampling they will not be excluded from the study.

Patients will be asked to perform one of their exercise sessions in the VUmc. This session will be guided by an experienced physical therapist. Both before and after the exercise we will collect 5ml blood in a serum tube. This will be done to measure Interleukine-6 levels (IL-6) from serum which is supposed to be present in elevated concentrations during- and directly after exercise and is part of the rationale for this study.

Fitness tests

Physical fitness will be assessed both prior to randomization and after two cycles of chemotherapy in the patient's own treating hospital, except for the patients from the Amstelland hospital.

- Aerobic fitness will be assessed during a submaximal endurance test performed on a cycle ergometer assessing the time that a patient can cycle at 70% of the estimated work load based on the steep ramp test, until a maximum of 30 min [3].
- Upper and lower body muscle strength will be assessed using the 1-repetition maximum for leg press and bench press according to standardized protocols.

Questionnaires

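### The closed list for expedited SAE reporting omits the fitness tests that every participant undergoes (and, as a minor point, the IL-6 venepunctures)

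*Protocol*

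**What the plan says.** Protocol section 7.2.2 sets the scope of SAE reporting to the METC: "the sponsor will report only the SAEs related to the exercise intervention, the blood sampling (T0 en T1) and the biopsy (T1". Fatal or life-threatening events go in within 7 days. It then adds: "All other SAEs will be reported within a period of maximum 15 days".

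Section 7.2.1 sets the scope of AE recording in different words: "all exercise-related AE's and AE's related to the biopsy (T1) and blood sampling (T0 en T1".

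The Summary says of the pre-treatment visit that "a blood sample and a fitness test will be performed in all participants". Section 6.3 gives the timing: "Physical fitness will be assessed both prior to randomization and after two cycles of chemotherapy". Table 1 in that section lists the aerobic part as "Steep ramp test & endurance test", marked at T0 and T1. Of the strength part, section 6.1.2 says: "Upper and lower body muscle strength will be assessed with the 1RM leg press and bench press according to standardized protocols".

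Sections 6.1.2 and 6.3 also describe IL-6 samples, taken before and directly after one training session. They are sought only from intervention patients at the Amsterdam UMC/VUmc, under a separate consent form.

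**The concern.** The SAE rule names individual procedures and closes the list with the word *only*, so a procedure that is not named is outside it. The fitness tests are not named. They include 1RM lifts, which are maximal by definition, and an endurance ride of up to 30 minutes. At T1 they are done after two or three chemotherapy cycles.

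At stake is prompt oversight. If a patient had a serious event during a baseline test, or a control patient had one during the T1 test, the sponsor could follow 7.2.2 to the letter and send no 7- or 15-day report.

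**Working it through.** The protocol gives no figure to reproduce here. The check compares each study procedure with the two lists, then counts the exposure.

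**Coverage**

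| Study procedure | Who and when | AE recording (7.2.1) | SAE reporting (7.2.2) |
|---|---|---|---|
| Exercise sessions | Exercise arm, 6 weeks | Covered | Covered |
| Study blood, T0 and T1 | All | Covered | Covered |
| Biopsy, T1 | All | Covered | Covered |
| Fitness tests, T0 and T1 | All | Not named; arguably within *exercise-related* | Not covered |
| IL-6 blood draws | Consenting exercise-arm patients, one centre | Not covered (sampling limited to T0 and T1) | Not covered |

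**Can the SAE list be read to include the fitness tests?**

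1. *As part of the exercise intervention.* Section 5.1 describes the intervention as supervised training sessions plus encouraged home activity. The first fitness test takes place before randomisation, when nobody has an intervention. Controls are tested at both time points and are assigned usual care for the six weeks between. The reading fails.
2. *Through the 15-day sentence.* That sentence follows the word *only* and a reference back to the listed SAEs. It therefore sets the deadline for listed events that are neither fatal nor life-threatening. Read as a catch-all, it would contradict the restriction in the same paragraph.
3. *Through section 7.3.* It asks for SAE reporting until the end of the study, but as the protocol defines it, which leads back to 7.2.2.
4. *Because the risk is negligible.* Section 9.3 applies that label to blood drawing and the fitness test in one sentence. Blood drawing at T0 and T1 is listed all the same, so the label does not explain the omission.

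**Exposure**

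Inputs: 20 patients (section 3); 2 time points (Table 1); 4 tests per occasion (steep ramp, endurance, leg press, bench press).

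- Test occasions: 20 × 2 = 40 at most. Drop-out would lower this, as section 6.5 allows no replacement.
- Single tests: 40 × 4 = 160 at most.
- Occasions without an assigned intervention: 20 at T0 + *c* at T1, where *c* is the number of controls. The allocation ratio is not stated. Under an assumed 1:1 split *c* = 10, giving 20 + 10 = 30, or 30/40 = 75%. The 20 at T0 do not depend on the ratio.
- IL-6 draws: at most 10 × 2 = 20 under the same assumption, and fewer in practice because only consenting patients from one centre contribute.

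These are counts of exposure. The protocol gives no event rate for the tests, so no expected number of SAEs can be derived.

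**The case against.** The strongest reply is that the METC would still hear of such events. Section 10.4 includes serious adverse events in the annual progress report without limiting them to listed procedures. Section 7.1 requires suspension and notification without undue delay if subject safety is jeopardised, whatever the cause. This stands. A reader might infer from 7.2.2 that serious harm from a fitness test would never reach the committee; the documents do not support that. What is missing is the 7/15-day route, which an annual summary does not replace.

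A second reply is that 7.2.1 records *exercise-related* events, and a collapse on a cycle ergometer or an injury in a 1RM lift is exercise-related in ordinary language, in either arm. This is plausible, so the study data would probably hold such events. It also shows the mismatch: the SAE section uses the narrower *exercise intervention*.

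Third, selective SAE reporting is a deliberate choice in a 20-patient study classed as negligible risk (section 10.2). That is fair, and it limits the weight of the point. It does not explain why T0/T1 blood sampling is listed and strenuous testing is not.

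Three further inferences should be resisted:

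- *That the tests serve research only.* Section 5.1 sets aerobic load from the steep ramp test and resistance load from the 1RM, so some of these measures also guide training in the exercise arm.
- *That the later RCT would reuse the tests, leaving its safety basis incomplete.* Section 6.3 says only that pilot data might be used in that trial.
- *That the IL-6 gap matters as much as the fitness-test gap.* A serious event from the session itself is already covered as exercise intervention. Only harm from two 5 ml venepunctures is outside the rule.

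**Conclusion.** The point holds for expedited SAE reporting. Section 7.2.2, followed as written, excludes serious events caused by the fitness tests, and no other passage brings them into the 7/15-day route. The gap covers every participant: up to 40 test occasions, about 30 of them without an assigned intervention if allocation is 1:1. The IL-6 venepunctures are a minor addition, outside the T0/T1 wording of both sections.

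The conclusion rests on reading *only* literally and on treating the fitness tests as assessments rather than intervention, which their timing and their use in controls support. It does not show that events would be lost from the study data or withheld from the METC altogether. It touches no endpoint, success criterion, estimate or sample size. It is a modest correction, worth making because a stated safety rule does not match the procedures the protocol itself prescribes.

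**What to change.** Reconcile sections 7.2.1 and 7.2.2 so that both use the same scope. Suggested wording for each: *events related to any study-specific procedure, namely the exercise intervention, the fitness tests (T0 and T1), all study blood sampling including the IL-6 samples, and the T1 biopsy*. In 7.2.2, also make clear that the 15-day deadline applies to SAEs within this scope that are neither fatal nor life-threatening.

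The cost is one sentence in each section, notified to the METC as an amendment under section 10.3, and very few extra reports. Treatment, assessments and analysis stay as they are.

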7.3 Follow-up of adverse events

All AEs will be followed until they have abated, or until a stable situation has been reached. Depending on the event, follow up may require additional tests or medical procedures as indicated, and/or referral to the general physician or a medical specialist. SAEs need to be reported till end of study within the Netherlands, as defined in the protocol

8. STATISTICAL ANALYSIS

8.1 Primary study parameter(s)

Information on trial feasibility and preliminary effects are crucial to set up a randomized controlled trial with sufficient statistical power to evaluate the exercise effects on immune cell infiltration into the tumor.

The *feasibility* will be assessed using the following descriptive statistics:

- The proportion of eligible patients who are willing to participate in this study and undergo an additional tumor biopsy.
- The percentage of tumor biopsies at baseline and after 6 weeks of neo-adjuvant treatment that can be assessed successfully.

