2. OBJECTIVES

Primary Objective: To study trial feasibility in terms of patient enrollment and the percentage of tumor biopsies that can be successfully assessed for changes in immune cell and NK cell content.

Secondary Objective(s): To study preliminary effects of exercise on immune cell function.

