3. STUDY DESIGN

This is a multicenter randomized controlled feasibility trial, in which 20 women with breast cancer scheduled for neoadjuvant 2 or 3 weekly AC-T(H) chemotherapy will be randomized into a combined aerobic and resistance exercise intervention group or a usual care (no exercise)

control group, during the first 6 weeks (2 or 3 cycles) of chemotherapy. Patients from the control group will receive care as usual and are requested to maintain their usual daily physical activities. In order to limit contamination (increase of exercise in the control group), non-participation and prevent dropout, the control group will be offered the same 6-week exercise intervention after the tumor biopsy has been taken after 6 weeks. The study design and timepoints of measurements are presented in Figure 2.

[figure not shown]

Figure 2. Study design and time-point of measurements

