6. METHODS

6.1 Study parameters/endpoints

6.1.1 Main study parameter/endpoint

Feasibility will be judged according to two key questions:

1) Recruitment

What is the proportion of eligible patients who are willing to participate in this study and undergo an additional tumor biopsy?

2) Quality of tumor material

What is the percentage of tumor biopsies that can be examined successfully both at baseline and after 6 weeks of neo-adjuvant treatment?

We define a biopsy as successful if we collected enough tumor tissue and the quality of the tissue enables us to perform IHC-analysis to determine the infiltration of NK-cells into the tumor.

We conclude that our feasibility-study is successful if:

1. we achieve a recruitment rate of at least 20%.
2. we can examine biopsies successfully on infiltration of NK-cells (both on T0 and T1) in 14 of 20 patients (70%).

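### Does the per-biopsy wording in Protocol 8.1 leave the 14-of-20 feasibility criterion without a matching statistic?

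*Protocol*

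**What the plan says.** Section 6.1.1 of the Protocol poses the second feasibility question as "What is the percentage of tumor biopsies that can be examined successfully both at baseline and after 6 weeks of neo-adjuvant treatment". Shortly afterwards it says how the answer is judged. The study succeeds on this item if "we can examine biopsies successfully on infiltration of NK-cells (both on T0 and T1) in 14 of 20 patients (70"%). The unit is the patient, both time points must be usable, and the denominator is 20.

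Section 8.1 lists the descriptive statistics for feasibility. Its second bullet reads "The percentage of tumor biopsies at baseline and after 6 weeks of neo-adjuvant treatment that can be assessed successfully". It omits the word 'both', gives no denominator and does not repeat the threshold. Section 2 uses similar shorthand: "the percentage of tumor biopsies that can be successfully assessed for changes in immune cell and NK cell content".

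Two further passages bear on the denominator. Under 6.3, when blood counts at T1 are too low, "patients will be excluded for the second biopsy because of an increased risk of procedure related hemorrhage or infection". Under 6.5, "In case of drop-outs, patients will not be replaced by including extra patients because feasibility of patient enrollment is one of the primary outcomes", and it adds: "This also includes patients with an infection at T1 and thereby an exclusion for the biopsy".

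**The concern.** Tumor material is one of the two items on which this pilot is judged. The section that names the primary statistics appears to name a different quantity from the one its threshold uses: biopsies in 8.1, patients with a usable pair in 6.1.1. The difference has a direction. With every planned biopsy counted, the share of usable biopsies can only equal or exceed the share of patients with a usable pair, so setting the former beside 70% would favour declaring success.

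Section 8.1 also does not say how to count a T1 biopsy that is never taken, which 6.3 expects to happen. If such biopsies dropped out of the denominator, the percentage could look better still. At stake is whether a reader of the results could tell that the criterion had been met.

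**Working it through.** **Inputs.** 20 patients (Section 3), hence at most 20 T0 and 20 T1 biopsies, 40 in all. Success rule: 14 of 20 patients with both usable (6.1.1), taken here as at least 14.

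**The plan's own figure.** 14/20 = 0.70, as stated.

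**From biopsies to pairs.** Let *a* be the usable T0 biopsies and *b* the usable T1 biopsies, each out of 20. The number of complete pairs lies between max(0, *a* + *b* − 20) and min(*a*, *b*). Taking all splits of a pooled total *S* = *a* + *b*:

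| Pooled usable biopsies | Possible pairs | 14-of-20 rule |
|---|---|---|
| 27/40 (67.5%) | 7 to 13 | not met |
| 28/40 (70%) | 8 to 14 | undetermined |
| 30/40 (75%) | 10 to 15 | undetermined |
| 32/40 (80%) | 12 to 16 | undetermined |
| 33/40 (82.5%) | 13 to 16 | undetermined |
| 34/40 (85%) | 14 to 17 | met |

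Separate percentages per time point have the same limit: 14/20 at each gives between 14 + 14 − 20 = 8 and 14 pairs. The lower end is an extreme pattern. It needs 6 patients to fail at T0 only, 6 to fail at T1 only, and none to fail at both (8 + 6 + 6 = 20). At the other extreme, if all 20 T0 biopsies were usable (an assumption; the protocol gives no rate), the T1 percentage out of 20 would equal the paired rate exactly.

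**Biopsies not taken.** Suppose, for illustration, that 8 patients have no T1 biopsy and every biopsy taken is usable. Counting biopsies taken gives (20 + 12)/32 = 32/32 = 100%. Counting pairs gives 12/20 = 60%, which fails the rule.

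So the two quantities do differ. Whether that matters depends on which one the protocol directs the analyst to compare with 70%.

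**Reading the sections side by side.**

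- The two bullets of 8.1 follow the two key questions of 6.1.1 in order. The first is nearly identical to its question and the second is a slightly shortened form. They restate the questions and define no rival endpoint.
- Key question 2 itself speaks of a percentage of biopsies, yet 6.1.1 resolves it into patients with both biopsies usable. The shorthand is explained where it is introduced.
- Section 2 speaks of assessing changes, which needs a T0 and a T1 sample from the same patient.
- Section 8.1 sets no threshold, no pooling and no denominator of 40. The only 70% for tumor material is the one in 6.1.1.
- With the rule fixed at 14 of 20 and drop-outs not replaced, a patient without a T1 biopsy cannot have both examined and so is not a success. The 32/32 reading is therefore closed off for the decision.

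**The case for a change.** The strongest case for a change is that 8.1 is where the primary statistics are named, and its ordinary reading is a count of biopsies. This is more than an omission that an SAP could fill, because the protocol states a statistic and states it differently from its own criterion. An SAP copied from 8.1 would carry the difference forward. The misreading always leans towards success. The ambiguous band of 28/40 to 33/40 starts exactly at the nominal 70%, and aligning the text would take one sentence.

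Much of this stands. The word 'both' is missing, the bounds are correct, and a reader given only a pooled percentage in that band could not tell whether the rule was met. What does not stand is the step from loose wording to a wrong or undecidable result. That step requires someone to form a pooled figure the protocol never mentions and compare it with 70% while ignoring the sentence that defines the 70%. It is also too strong to say the quantities cannot be compared: 27/40 or fewer rules success out, and 34/40 or more guarantees it. The same shorthand in Section 2 misleads nobody, because the meaning is fixed in 6.1.1.

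**Conclusion.** The inconsistency is real but clerical, and no change to the plan follows. The success rule is explicit, paired and based on 20 patients, and it governs the feasibility decision. The data needed to apply it are the same data that 8.1 describes: whether each patient's T0 and T1 biopsies could be examined. Counting complete pairs is a sensible completion of the 8.1 bullet, and percentages per time point can stand beside that count as description.

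A per-biopsy percentage on its own would leave the rule undetermined from 28/40 to 33/40, but it is not the quantity that is tested, so the effect on the go/no-go conclusion is nil. This rests on two readings: that 6.1.1 prevails over the shorter wording in 8.1, and that the denominator stays at 20 when a T1 biopsy is withheld or missed. The text of 6.1.1 and 6.5 supports both.
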